## 7 STUDY INTERVENTION DISCONTINUATION AND PARTICIPANT DISCONTINUATION/WITHDRAWAL

### 7.1 DISCONTINUATION OF STUDY INTERVENTION

#### 7.1.1 DISCONTINUATION OF A PARTICIPANT'S ASSIGNED INTERVENTION

Participants will be monitored for safety during the trial and the occurrence of certain adverse events or laboratory abnormalities will result in discontinuation from the participant's current treatment; that is, participation in the current treatment period will stop, and the participant will enter the washout period. The following adverse events or lab abnormalities will result in discontinuation from the participant's current treatment:

1. Serious infection (including pneumonia, cellulitis, kidney or neurologic infections, and any bacteremia/sepsis).
2. Any bleeding event thought to be associated with a platelet count reduction per the judgment of the center investigator.
3. Any other adverse event, per judgment of the center investigator, requiring discontinuation from treatment.
4. Laboratory values are monitored per the schedule of activities in Section 1.3. For adults, the below lab tests will be assessed at every 4-week visit during the treatment period. Abnormalities in the following laboratory values require prompt retesting within 3 to 5 days:
  - ANC <1000/ $\mu$ L for black participants, <1500/ $\mu$ L for other participants.
  - Lymphocyte count <500/mm^3.
  - Platelet count <50,000/mm^3.
  - Hemoglobin <9.0 g/dL.
  - AST and/or ALT elevation >3 times the upper limit of normal.
  - Bilirubin  $\geq$ 2 times the upper limit of normal.
  - Calculated eGFR < 54 mL/min/1.73 m^2 and baseline eGFR was >60 mL/min/1.73 m^2 OR calculated eGFR < 50 mL/min/1.73 m^2 and baseline eGFR was 54-60 mL/min/1.73 m^2

If both tests violate the following cut-off values, the participant is removed from treatment:

- a. Two sequential platelet counts <50,000/mm^3.
- b. One platelet count <25,000/mm^3 unless the confirmatory test demonstrates a count >50,000/mm^3. Treatment must be withheld pending the confirmatory retest.
- c. Two sequential neutrophil counts <500/mm^3.
- d. Two sequential lymphocyte counts <500/mm^3.
- e. Two sequential hemoglobin assessments <8.0 g/dL or >30% below the participant's initial baseline value or the baseline value for the current treatment period.
- f. Two sequential AST or ALT elevations >3 times the upper limit of normal with at least one total bilirubin value  $\geq$ 2 times the upper limit of normal.
- g. Two sequential AST or ALT elevations >3 times the upper limit of normal accompanied by symptoms consistent with hepatic injury, per the judgment of the center investigator.

- h. Two sequential AST or ALT elevations >5 times the upper limit of normal, regardless of total bilirubin or accompanying symptoms.
- i. Two sequential decreases in eGFR < 54 mL/min/1.73 m^2 and baseline eGFR was >60 mL/min/1.73 m^2 OR eGFR < 50 mL/min/1.73 m^2 and baseline eGFR was 54-60 mL/min/1.73 m^2
- 5. Any safety issue that has required or will require (per the investigator's judgment) interruption to treatment for >28 days.
- 6. Any event (i.e. asthma exacerbation, asthma treatment, or any other medical condition) requiring 21 or more contiguous days of prednisone above the participant's usual baseline dose.

Specific interventions may have additional safety criteria for discontinuing treatment (see appendices).

A participant will be discontinued from treatment if, during an exacerbation, he/she

- Is admitted to an ICU and requires non-invasive positive pressure ventilation or
- Experiences three exacerbations during a treatment period.

If, following treatment discontinuation for any of the criteria listed above, participants are deemed eligible (by safety criteria) to continue in the study, they will enter the 8-week (or longer) washout period preceding the next intervention. Entry into the washout period will begin at least 7 days after completing treatment of the exacerbation with oral or parenteral corticosteroids.

Participants who respond to treatment with systemic corticosteroids or who receive a single IM injection of steroid at the beginning of an exacerbation will not be discontinued from treatment, unless this is their 3rd exacerbation within the same treatment period, in which case, the above treatment discontinuation criteria apply.

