\*Visit SC is optional. All other visits are approximately 4 weeks apart. Treatment visits X.1-X.6 are repeated each treatment period.

These procedures and assessments may be conducted remotely via phone, videoconference or electronic survey methods.

 Spirometry may be conducted in the home and/or in the clinic.

 Optional at site discretion to demonstrate reversibility

 Not required for adolescents at VX.2 and VX.4.

 Blood for TB via QuantiFERON is collected on adults only

 If not collected before V1.1, the Sputum and CT can be collected before or at V2.1 or before or at V3.1.

Sputum induction and CT scans may not be conducted at all sites.

 PBMCs may not be collected at all sites.

 PBMC is only collected at V1.1.

 Blood for RNA if not collected before V1.1, should be collected at V2.1, and, again, at V3.1.

 Nasal EPX can be skipped if the institution requires a COVID test before the procedure. Nasal EPX collection is optional at the site level.

 Not required at the final VX.6.

Note: Due to the COVID-19 pandemic, not all procedures will be conducted at all clinic visits.

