### **Safety Exclusion Criteria**

Participants who meet the following criteria will be excluded from the study:

- Hemoglobin < 10 g/dL
- ANC <1000/ $\mu$ l for black participants, <1500/ $\mu$ l for other participants
- Lymphocytes <500/ $\mu$ l
- Platelet count <100,000/ $\mu$ l
- ALT/AST >2x ULN
- Bilirubin  $\geq$ 2x ULN
- Estimated glomerular filtration rate (eGFR) <54 ml/min/1.73 sq m on two sequential tests performed within 2-4 weeks OR eGFR 54-60 ml/min/1.73 sq m and proteinuria detected on urine dipstick
- Positive Human Immunodeficiency Virus, Types 1 & 2 (HIV 1&2) Ab/Ag immunoassay followed by a confirmatory positive test (Geenius™ HIV-1/HIV-2 antibody differentiation immunoassay)
- Positive Hepatitis B surface Ag (active infection) or Hepatitis B core total antibody (marker of past infection that could reactivate)
- Positive Hepatitis C RNA test following positive Hepatitis C Antibody
- EKG with significant clinical findings

Adult participants (age $\geq$ 18) will be screened for TB. A positive QuantiFERON-TB Gold test requires further screening. A participant may be included in PrecISE if at least one of the following criteria are met:

- A chest radiograph (CXR) done within the last six months of the test that shows no evidence of active TB

- A chest CT scan done within the last six months of the test showing no evidence of active TB
- Documentation of adequate treatment for latent TB.

In cases of an indeterminate QuantiFERON-TB test result, a second blood specimen must be drawn. A chest x-ray is not required if the participant has a negative QuantiFERON-TB Gold test.

Adolescent participants (age<18) will not be screened for TB.

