**Other criteria for participant discontinuation at any point in the study:**

1. Safety laboratory exclusions as defined in Sections 5.2 and 7.1 that do not resolve in the washout phase that in the judgment of the site physician or Safety Committee constitutes an on-going safety risk for the participant.
2. Participant or parent of participant (for children) withdraws consent or child withdraws assent.
3. Participant becomes pregnant.
4. Study physician determines that continuation in the study is not in the best interest of the participant.
5. Participant suffers life-threatening asthma exacerbation. A life-threatening asthma exacerbation is defined as an ICU admission requiring intubation, hypoxic seizure or loss of consciousness.
6. Frequent asthma exacerbations
  - a. For participants with 3 or fewer asthma exacerbations in the prior year at screening, the participant has five or more exacerbations in one year of the study.
  - b. For participants with 4 or more asthma exacerbations in the prior year at screening, the participant has a 50 percent or greater increase in exacerbations in one year of the study, compared to the prior year at screening.
7. Frequent hospitalizations
  - a. For participants who have 3 or fewer hospitalizations in the prior year at screening, the participant has four or more hospitalizations (greater than 24 hours) in one year of the study.
  - b. For participants who have 4 or more hospitalizations in the prior year at screening, the participant has a 50 percent or greater increase in hospitalizations in one year of the study, compared to the prior year at screening.
8. Participant has a major change in therapy (see Section 6.5.4).

As always, the participant can withdraw consent from the master protocol at any point, and that will lead to discontinuation from the study. At that point, the investigator will make reasonable effort to ensure participant's well-being and safety and provide a termination visit with appropriate documentation.

The site investigator may decide to stop a participant's treatment due to side effects or other safety concerns. In that case, the participant would immediately begin the washout phase and then receive the treatment assigned according to their initial crossover sequence (period 2), or be re-randomized for the next treatment (period 3-6). If a participant elects to withdraw their consent from a treatment, this will result in discontinuation from the entire study.

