7.6 Safety Data Analyses

Safety data are evaluated on an ongoing basis. Monthly reports of serious adverse events (SAEs) are provided to all DSMB members, and more comprehensive reports of safety data are provided to the DSMB members for review and discussion at their quarterly meetings. These reports include incidence of treatment-emergent adverse events by assigned treatment group. Adverse events are coded using the Medical Dictionary for Regulatory Activities (MedDRA). Adverse event rates (and severity of non-serious adverse events) are compared between active and placebo periods for each intervention. Note that for a particular intervention, all placebo periods for participants receiving the intervention are included, and not just those where the matching placebo was received.

Based on the results of their review, the DSMB will recommend to the NHLBI whether to continue or discontinue each intervention for safety reasons. In addition, the DSMB monitors all safety data

throughout the course of the trial and will be notified as soon as possible of any SAE that is deemed both unexpected and probably related to treatment (serious, unexpected, suspected adverse reactions or SUSARs).

The PrecISE Medical Monitor reviews lab abnormalities on an ongoing basis that are potentially unblinding to clinical personnel at the site and advises the clinical investigator and staff if follow-up testing or other procedures are needed. Summaries of lab abnormalities are reviewed by the DSMB at their quarterly meetings.

Final safety analyses will be performed for each intervention, once the intervention completes and all follow-up data are obtained. Descriptive summaries (differences from placebo and corresponding 95% confidence intervals, tables and graphs) of safety endpoints, including adverse events, laboratory parameters, and other safety biomarkers, will be generated by test treatment versus placebo.

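### A haemoglobin fall of more than 30% that stays at or above 9.0 g/dL meets a removal cut-off but orders no prompt retest

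*Protocol*

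**What the plan says.** Item 4 of Protocol 7.1.1 works with two lists. The first sets retest triggers: "Abnormalities in the following laboratory values require prompt retesting within 3 to 5 days". Its haemoglobin entry is "Hemoglobin <9.0 g/dL" and nothing more. The second sets the cut-offs that remove a participant from treatment when both tests violate them. Rule (e) in that list is "Two sequential hemoglobin assessments <8.0 g/dL or >30% below the participant's initial baseline value or the baseline value for the current treatment period".

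Entry excludes "Hemoglobin < 10 g/dL" (Protocol 5.2, Safety Exclusion Criteria) and sets no upper limit. Adults have a blood count at every 4-week treatment visit. For adolescents, footnote 4 of the Schedule of Activities (Protocol 1.3) marks the count as "Not required for adolescents at VX.2 and VX.4", so X.3 is the only required count between X.1 and X.5.

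Two discretionary routes exist. Protocol 7.2 says "The site investigator may decide to stop a participant's treatment due to side effects or other safety concerns". SAP 7.6 says the Medical Monitor reviews potentially unblinding laboratory abnormalities and "advises the clinical investigator and staff if follow-up testing or other procedures are needed".

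**The concern.** A two-test stopping rule works quickly only if the first qualifying value prompts the second test. Rule (e) has an absolute arm (below 8.0 g/dL) and a relative arm (more than 30% below baseline). The absolute arm sits wholly inside the retest trigger. The relative arm does not: a participant who starts high enough can lose over 30% of their haemoglobin and still be at or above 9.0 g/dL.

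Such a participant has met a stated stopping threshold once, yet the master protocol requires nothing until the next scheduled count. At stake is time on study drug after a qualifying safety signal. The efficacy analyses are not touched.

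**Working it through.** **Inputs.** Retest trigger: below 9.0 g/dL, repeat in 3 to 5 days (Protocol 7.1.1 item 4). Removal: below 8.0 g/dL, or more than 30% below the initial or current-period baseline, on two sequential tests (7.1.1, rule e). Entry floor: 10 g/dL (5.2). Visit spacing: about 4 weeks (1.3). Adolescent counts on treatment: X.3 and X.5 (1.3, footnote 4).

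**Step 1: where the gap opens.** A fall of more than 30% means a value below 0.70 × baseline. It escapes the retest when 9.0 ≤ value < 0.70 × baseline. That needs a baseline above 9.0/0.70 = 12.86 g/dL. From the entry floor of 10 up to 12.86, every fall of more than 30% is already below 9.0, and the two lists agree.

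**Step 2: width of the gap.**

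| Baseline (g/dL) | 0.70 × baseline | First values meeting the relative cut-off with no retest |
|---|---|---|
| 12 | 8.4 | none |
| 13 | 9.1 | 9.0 to <9.1 |
| 14 | 9.8 | 9.0 to <9.8 |
| 15 | 10.5 | 9.0 to <10.5 |
| 16 | 11.2 | 9.0 to <11.2 |

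For example, 15.0 falling to 10.4 is a drop of 4.6/15.0 = 30.7%. It meets the cut-off and orders nothing.

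**Step 3: the delay.** This step takes consecutive scheduled counts as satisfying rule (e).
- Adults: a first value at X.2, X.3 or X.4 (weeks 4, 8, 12) is confirmed at week 8, 12 or 16, so 28 days later. Against a retest in 3 to 5 days, the excess is 28 − 5 = 23 to 28 − 3 = 25 days.
- Adolescents: a first value at X.3 (week 8) is confirmed at X.5 (week 16), so 56 days later. The excess is 56 − 5 = 51 to 56 − 3 = 53 days.
- When the first value comes at X.4 in an adult or X.3 in an adolescent, confirmation falls at the end-of-treatment visit, when removal has little effect.

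**Step 4: are the other removal rules different?**

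| Removal cut-off | Retest trigger | Inside the trigger? |
|---|---|---|
| Platelets <50,000 and <25,000 | <50,000 | yes |
| Neutrophils <500 | <1000 or <1500 | yes |
| Lymphocytes <500 | <500 | yes, identical |
| AST/ALT >3× and >5× ULN | >3× ULN | yes |
| eGFR, dependent on baseline | same criterion | yes, identical |
| Haemoglobin <8.0 | <9.0 | yes |
| Haemoglobin >30% below baseline | <9.0 | not above baseline 12.86 |

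The eGFR line is the telling one. Its removal rule begins "Two sequential decreases in eGFR < 54 mL/min/1.73" and depends on baseline, and the retest line repeats the same criterion. The haemoglobin line is the only one where this was not done, and no reason is given.

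**The case against.** The strongest objection concerns the words introducing the removal list. If both tests means the triggering test and its 3-to-5-day repeat, item 4 is a two-step procedure that starts only below 9.0 g/dL. The relative arm would still do some work: between baselines of 8.0/0.70 = 11.43 and 12.86 it removes some participants with values from 8.0 to 9.0, and above 12.86 it removes everyone confirmed below 9.0. A value of 9.5 from a baseline of 14 would never enter the procedure, so there would be no 28- or 56-day delay to measure. This does make the delay figures depend on the reading. It does not rescue the rule: on this reading the relative arm has no effect at all at or above 9.0 g/dL, which is worse than a delay.

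Other points stand as limits:
- Appendices I–V were not available. Protocol 6.3, 7.1.1 and 8.2 allow intervention-specific monitoring, laboratory tests and stopping criteria, so actual testing intervals for a given agent may be shorter.
- The 56-day figure applies only to adolescents, who can receive only MCT or Broncho-Vaxom (SAP 1.1). About 40 are expected (SAP 7.9.2).
- Adverse-event follow-up, investigator judgment, the Medical Monitor and quarterly DSMB review could each lead to earlier action. None of them mandates a prompt retest, and SAP 7.6 does not say whether haemoglobin falls count as potentially unblinding.
- The documents contain no haemoglobin data showing how often this window would be entered.

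**Conclusion.** The concern holds. For baselines above 12.86 g/dL, the master protocol has a band of haemoglobin values that meet a removal cut-off but order no prompt retest. The band widens from nothing at 12.86 to 9.0–<11.2 g/dL at a baseline of 16.

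If consecutive scheduled counts satisfy rule (e), the cost is a nominal 23 to 25 extra days on treatment in adults and 51 to 53 in adolescents. If only a triggered retest counts, the relative arm does not operate in that band. Both statements assume visits on the nominal 4-week schedule, no additional rule in the unseen appendices, and no discretionary action.

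This is a modest, easily corrected safety gap. Values below 9.0 g/dL are retested in everyone, the number of participants affected is unknown, and no efficacy result or error rate changes.

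**What to change.** Extend the haemoglobin retest line in 7.1.1 item 4 to read: *Hemoglobin <9.0 g/dL, or more than 30% below either the initial baseline or the baseline of the current treatment period*. Keep the same 3-to-5-day retest and state that it applies to adults and adolescents. Leave rule (e) as it is.

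The trigger then becomes a value below max(9.0, 0.70 × baseline), taking the higher of the two baselines: 9.1 g/dL at baseline 13, 9.8 at 14, 10.5 at 15 and 11.2 at 16. This closes the band exactly under either reading of the removal sentence.

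The change is one line plus a few repeat blood counts, but a protocol change also needs agreement from the IND sponsor and NHLBI, FDA review and IRB approval (Statement of Compliance). This protocol version is dated 27 September 2024 and SAP 3.5.2 expects the last on-treatment visit in December 2024, so the benefit to current participants may be small. A short safety memo to sites would suit that timing, with the corrected line carried into any later amendment.

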#### 7.1.2 DISCONTINUATION OF AN INTERVENTION FROM THE MASTER PROTOCOL

The DSMB will review accumulating data throughout the study to determine if an intervention should be terminated from the PrecISE study for safety reasons. Interventions may also be discontinued from the study based on the interim futility analyses planned for the trial. Rules for termination for specific interventions due to safety may be required and, if so, will be specified in the appendix to this protocol for the intervention. If an intervention is discontinued from the study for either futility or safety reasons, participants who are receiving the intervention or its matching placebo will immediately begin an 8-week (or longer) washout phase and be re-randomized to another treatment.

#### 7.1.3 DISCONTINUATION OF THE STUDY

At this time, we do not anticipate there will be a reason to stop the entire PrecISE study, with the exceptions of termination of funding by NHLBI or poor recruitment to the point where the study is highly unlikely to meet its goals.

### 7.2 PARTICIPANT DISCONTINUATION/WITHDRAWAL FROM THE STUDY

A participant may be discontinued from the study if he/she is shown to not meet the inclusion criteria based on new information that was not available at the time of initial enrollment (e.g. uncovering a diagnosis of another lung disease), and continuing in the study poses a safety risk. Participants should not be discontinued for reasons other than new information that constitutes a safety risk. For example, if new information indicates that a participant meets one of the exclusion criteria for a test treatment, but the criteria does not pose a safety risk to the participant, then the participant should not be

discontinued. In this case, the participant will be considered in violation of the protocol for that period and excluded from the per protocol analysis (see Section 9.4). In general, participants with poor compliance but at no increased risk will continue in the study to complete all study assessments and minimize attrition.

**Other criteria for participant discontinuation at any point in the study:**

1. Safety laboratory exclusions as defined in Sections 5.2 and 7.1 that do not resolve in the washout phase that in the judgment of the site physician or Safety Committee constitutes an on-going safety risk for the participant.
2. Participant or parent of participant (for children) withdraws consent or child withdraws assent.
3. Participant becomes pregnant.
4. Study physician determines that continuation in the study is not in the best interest of the participant.
5. Participant suffers life-threatening asthma exacerbation. A life-threatening asthma exacerbation is defined as an ICU admission requiring intubation, hypoxic seizure or loss of consciousness.
6. Frequent asthma exacerbations
  - a. For participants with 3 or fewer asthma exacerbations in the prior year at screening, the participant has five or more exacerbations in one year of the study.
  - b. For participants with 4 or more asthma exacerbations in the prior year at screening, the participant has a 50 percent or greater increase in exacerbations in one year of the study, compared to the prior year at screening.
7. Frequent hospitalizations
  - a. For participants who have 3 or fewer hospitalizations in the prior year at screening, the participant has four or more hospitalizations (greater than 24 hours) in one year of the study.
  - b. For participants who have 4 or more hospitalizations in the prior year at screening, the participant has a 50 percent or greater increase in hospitalizations in one year of the study, compared to the prior year at screening.
8. Participant has a major change in therapy (see Section 6.5.4).

As always, the participant can withdraw consent from the master protocol at any point, and that will lead to discontinuation from the study. At that point, the investigator will make reasonable effort to ensure participant's well-being and safety and provide a termination visit with appropriate documentation.

The site investigator may decide to stop a participant's treatment due to side effects or other safety concerns. In that case, the participant would immediately begin the washout phase and then receive the treatment assigned according to their initial crossover sequence (period 2), or be re-randomized for the next treatment (period 3-6). If a participant elects to withdraw their consent from a treatment, this will result in discontinuation from the entire study.

